5.1.3 Subject Exclusion Criteria

The subject must be excluded from participating in the trial if the subject:

1. Is currently participating in or has participated in a study of an investigational agent (except glutamine) or using an investigational device within 2 weeks of the first dose of treatment.
2. Has a diagnosis of immunodeficiency or is receiving systemic steroid therapy or any other form of immunosuppressive therapy within 7 days prior to the first dose of trial treatment. With the exception of physiologic steroid replacement.
3. Has had a prior monoclonal antibody within 2 weeks prior to study Day 1 or who has not recovered (i.e., \leq Grade 1 or at baseline) from adverse events due to agents administered more than 4 weeks earlier.
4. Has had prior chemotherapy, targeted small molecule therapy, within 2 weeks prior to study Day 1 or who has not recovered (i.e., \leq Grade 1 or at baseline) from adverse events due to a previously administered agent. Prior radiation does not require a washout period.
 - Note: Subjects with \leq Grade 2 neuropathy are an exception to this criterion and may qualify for the study.
 - Note: If subject received major surgery, they must have recovered adequately from the toxicity and/or complications from the intervention prior to starting therapy.
5. Has a known additional malignancy that is progressing or requires active treatment. Exceptions include basal cell carcinoma of the skin, squamous cell carcinoma of the skin, or in situ cervical cancer that has undergone potentially curative therapy.
6. Has known active central nervous system (CNS) metastases and/or carcinomatous meningitis. Subjects with previously treated brain metastases may participate provided they are stable (without evidence of progression by imaging for at least four weeks prior to the first dose of trial treatment and any neurologic symptoms have returned to baseline), have no evidence of new or enlarging brain metastases, and are not using steroids for at least 7 days prior to trial treatment.
7. Has an active autoimmune disease requiring systemic treatment within the past 3 months or a documented history of clinically severe autoimmune disease, or a syndrome that requires systemic steroids or immunosuppressive agents. Subjects with vitiligo or resolved childhood asthma/atopy would be an exception to this rule. Subjects that require intermittent use of bronchodilators or local steroid injections would not be excluded from the study. Subjects with hypothyroidism stable on hormone replacement or Sjorgen's syndrome will not be excluded from the study.
8. Has evidence of interstitial lung disease or active, non-infectious pneumonitis.
9. Has an active infection requiring systemic therapy.

10. Has a history or current evidence of any condition, therapy, or laboratory abnormality that might confound the results of the trial, interfere with the subject's participation for the full duration of the trial, or is not in the best interest of the subject to participate, in the opinion of the treating investigator.
11. Has known psychiatric or substance abuse disorders that would interfere with cooperation with the requirements of the trial.
12. Is pregnant or breastfeeding, or expecting to conceive or father children within the projected duration of the trial, starting with the pre-screening or screening visit through 120 days after the last dose of trial treatment.
13. Has received prior therapy with an anti-PD-1, anti-PD-L1, anti-PD-L2, anti-CD137.
14. Has a known history of Human Immunodeficiency Virus (HIV) (HIV 1/2 antibodies).
15. Has known active Hepatitis B (e.g., HBsAg reactive) or Hepatitis C (e.g., HCV RNA [qualitative] is detected).
16. Has received a live vaccine within 30 days prior to the first dose of trial treatment.

5.2 Trial Treatments

The treatment to be used in this trial is outlined below.

Table 2 Trial Treatment

Drug	Dose/Potency	Dose Frequency	Route of Administration	Regimen/Treatment Period	Use
MK-3475	70-200 mg	Q 3 weeks	IV infusion	16 cycles	Experimental
The MK-3475 dosing interval may be increased due to toxicity as described in Section 5.2.1.2.					

5.2.1 Dose Selection/Modification

5.2.1.1 Dose Selection

The rationale for selection of doses to be used in this trial is provided in Section 4.0 – Background and Rationale.

The dose amount required to prepare the MK-3475 infusion solution will be based on the dose level which a patient is being treated on as per table 1.

Radiation will be given as per our institutional standard. For the patient in the LS-SCLC arm we will use 45Gy delivered BID over 15 days (we will allow a GTV boost to 54Gy, as long as the PTV dose remains at 45Gy). For patients with ES-SCLC we will use a dose of 45Gy daily (we will allow at GTV boost dose to 52.5Gy, as long as the PTV dose remains at 45Gy).

5.2.1.2 Dose Modification

MK-3475 will be withheld for drug-related Grade 4 hematologic toxicities, non-hematological toxicity \geq Grade 3 including laboratory abnormalities, and severe or life-threatening AEs as per Table 3 below.

Table 3: Dose modification guidelines for drug-related adverse events.

Toxicity	Grade	Hold Treatment (Y/N)	Timing for restarting treatment	Dose/Schedule for restarting treatment	Discontinue Subject (after consultation with Sponsor)
Hematological Toxicity	1, 2, 3	No	N/A	N/A	N/A
	4	Yes	Toxicity resolves to Grade 0-1 or baseline	May increase the dosing interval by 1 week	Toxicity does not resolve within 12 weeks of last infusion Permanent discontinuation should be considered for any severe or life-threatening event
Non-hematological toxicity	1	No	N/A	N/A	N/A
	2	Consider withholding for persistent symptoms	Toxicity resolves to Grade 0-1 or baseline	Clinical AE resolves within 4 weeks: Same dose and schedule (reference Section 5.6.1.2 for recommendations regarding pneumonitis) Clinical AE does not resolve within 4 weeks: May increase the dosing interval by 1 week for each occurrence	Toxicity does not resolve within 12 weeks of last infusion

Note: Exception to be treated similar to grade 1 toxicity

- Grade 2 alopecia
- Grade 2 fatigue

For additional information regarding Adverse Events with a potential Immune-Etiology reference Section 5.6.1.1.

Toxicity	Grade	Hold Treatment (Y/N)	Timing for restarting treatment	Dose/Schedule for restarting treatment	Discontinue Subject (after consultation with Sponsor)
	3, 4	Yes	Toxicity resolves to Grade 0-1 or baseline	May increase the dosing interval by 1 week for each occurrence	Toxicity does not resolve within 12 weeks of last infusion Permanent discontinuation should be considered for any severe or life-threatening event

In case toxicity does not resolve to Grade 0-1 within 12 weeks after last infusion, trial treatment should be discontinued after consultation with the Sponsor. With investigator and Sponsor agreement, subjects with a laboratory adverse event still at Grade 2 after 12 weeks may continue treatment in the trial only if asymptomatic and controlled. For information on the management of adverse events, see Section 5.6.1.

Subjects who experience a recurrence of the same severe or life-threatening event at the same grade or greater with re-challenge of MK-3475 should be discontinued from trial treatment.

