5.6.1.1 Supportive Care Guidelines for Events of Clinical Interest and Immune-related Adverse Events (irAEs) (Appendix 13.4)

Events of clinical interest of a potential immunologic etiology (irECIs) may be defined as an adverse event of unknown etiology, associated with drug exposure and is consistent with an immune phenomenon. irAEs may be predicted based on the nature of the MK-3475 compound, its mechanism of action, and reported experience with immunotherapies that have a similar mechanism of action. Special attention should be paid to AEs that may be suggestive of potential irAEs. An irAE can occur shortly after the first dose or several months after the last dose of treatment.

If an irAE is suspected, efforts should be made to rule out neoplastic, infectious, metabolic, toxin or other etiologic causes prior to labeling an adverse event as an irAE. Information on how to identify and evaluate irAEs has been developed and is included in the Event of Clinical Interest and Immune-Related Adverse Event Guidance Document located in the Administrative Binder. Subjects who develop a Grade 2 or higher irAE should be discussed immediately with the Sponsor.

Recommendations to managing irAEs not detailed elsewhere in the protocol are detailed in Table 6.

Table 6 General Approach to Handling irAEs

irAE	Withhold/Discontinue MK-3475?	Supportive Care
Grade 1	No action	Provide symptomatic treatment
Grade 2	May withhold MK-3475	Consider systemic corticosteroids in addition to appropriate symptomatic treatment
Grade 3 and Grade 4	Withhold MK-3475 Discontinue if unable to reduce corticosteroid dose to < 10 mg	Systemic corticosteroids are indicated in addition to appropriate symptomatic treatment. May utilize 1 to 2 mg/kg prednisone or equivalent per day.

	per day prednisone equivalent within 12 weeks of toxicity	Steroid taper should be considered once symptoms improve to Grade 1 or less and tapered over at least 4 weeks.
--	---	--

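### Tables 3 and 6 leave restart of MK-3475 open after severe immune events for which Appendix 13.4 says stop permanently, and the protocol body does not state which rule governs

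*Combined protocol and SAP*

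**What the plan says.** **Table 3 (section 5.2.1.2).** The lead sentence begins "MK-3475 will be withheld for drug-related Grade 4 hematologic toxicities, non-hematological toxicity" (of grade 3 or above) and ends "and severe or life-threatening AEs as per Table 3 below". The table gives no hold for hematologic toxicity of grade 1-3. It holds for hematologic grade 4 and non-hematologic grade 3-4, and gives recovery to grade 0-1 or baseline as the condition for restarting. A stop follows if toxicity has not resolved within 12 weeks of the last infusion. Otherwise: "Permanent discontinuation should be considered for any severe or life-threatening event". A note adds: "For additional information regarding Adverse Events with a potential Immune-Etiology reference Section 5.6.1.1".

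**Table 6 (section 5.6.1.1).** The section heading cites the appendix without ranking it: "Supportive Care Guidelines for Events of Clinical Interest and Immune-related Adverse Events (irAEs) (Appendix 13.4". The scope is set by "Recommendations to managing irAEs not detailed elsewhere in the protocol are detailed in Table 6". At grade 2 MK-3475 may be withheld. At grade 3-4 it is withheld, with one mandatory stop: "Discontinue if unable to reduce corticosteroid dose to < 10 mg" per day of prednisone equivalent within 12 weeks.

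**Appendix 13.4 (guidance document on events of clinical interest).** Its Overview defines discontinue as permanent and hold as leaving resumption open. Sections 3.4 (hematologic, grade 4), 3.5 (hepatic, grades 3 and 4), 3.6 (neurologic, grades 3-4) and 3.8 (renal, grades 3-4) say discontinue. Section 3.4 says hold at grades 2 and 3. The Overview limits its treatment advice to events judged related to the drug, calls that advice guidelines subject to clinical judgment, and refers dose-modification questions to the protocol's wording.

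**The concern.** The question is whether a patient is re-exposed to a PD-1 antibody after a severe immune event in the liver, kidney, nervous system or blood. An investigator working from Tables 3 and 6 may restart after recovery. One working from the appendix, to which the body itself refers in sections 5.6.1, 5.6.1.1, 7.1.2.1 and 7.2.3.2, stops for good. A second, smaller issue is that the two body tables disagree on whether to hold at all for a grade 3 immune hematologic event. This is a matter of patient safety and of uniform conduct in a trial whose primary endpoint is safety. It is not a matter of sample size or error rates.

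**Working it through.** No arithmetic applies beyond a count, so the texts are set side by side for events judged related to MK-3475.

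| Event and grade | Table 3 | Table 6 | Appendix 13.4 |
|---|---|---|---|
| Listed hematologic disorder, grade 2 | no hold | may withhold | hold (3.4) |
| Listed hematologic disorder, grade 3 | no hold | withhold | hold, stop to be considered (3.4) |
| Listed hematologic event, grade 4 | hold, restart possible | withhold, stop if taper fails | permanent stop (3.4) |
| Hepatic, grades 3 and 4 | hold, restart possible | withhold, stop if taper fails | permanent stop (3.5) |
| Neurologic, grades 3 and 4 | hold, restart possible | withhold, stop if taper fails | permanent stop (3.6) |
| Renal, grades 3 and 4 | hold, restart possible | withhold, stop if taper fails | permanent stop (3.8) |

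**Restart against stop.** Grade 4 hematologic gives 1 combination. Three organ classes at two grades give 3 × 2 = 6. The total is 1 + 6 = 7. Section 3.4 of the appendix defers to the protocol at grade 4 only for hematologic malignancies. For solid tumors, which include small cell lung cancer, it says stop.

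**Hold against no hold.** This concerns the disorders listed in section 3.4 (autoimmune hemolytic anemia, aplastic anemia, DIC, HUS, ITP, TTP), not cytopenia in general. At grade 3, Table 6 and the appendix agree, so Table 3 is the outlier. The lead sentence of 5.2.1.2 does not settle it: it withholds for severe events, but by reference to Table 3, whose grade 3 hematologic row says no.

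**The count is not exhaustive.** The appendix also says discontinue at grade 4 for endocrine (3.3), ocular (3.7), skin (3.9) and other (3.10) events. Differences run the other way too. Section 5.6.1 stops permanently at grade 3 enterocolitis, where appendix section 3.2 holds. Tables 3 and 6 hold for grade 3-4 hypothyroidism, where appendix section 3.3 lets dosing continue. Under the same thyroid heading, however, section 3.3 has a grade 4 discontinue entry that is not limited to hyperthyroidism, so grade 4 hypothyroidism is unclear. Pneumonitis (Table 7 and appendix section 3.1) is consistent on hold and stop.

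**Which text governs.** The only precedence statement found is the one in the appendix Overview, and it favors the protocol. Three things blur it: neither 5.2.1.2 nor 5.6.1.1 repeats it; the appendix is itself section 13.4 of the protocol, so Table 6's limit to events not covered elsewhere can be read as yielding to it; and the same Overview presents the appendix as directing when to hold or stop for each immune event.

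**The case against.** The strongest reply is that a hierarchy exists. The appendix defers to the protocol on dose modification, describes its content as guidelines, and elsewhere treats the protocol as a separate document (for example in its sections 2, 3.4 and 3.11). This stands. A reader might infer that the documents give no rule of precedence; they do not support that. On a plain reading the body governs, and what remains is doubt from Table 6's scope wording and from the body's silence. That reading also means the less protective rule applies in the seven combinations.

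A second reply is that the body permits restart but never requires it, so an investigator who stops permanently satisfies both texts. This also stands. It would be wrong to infer that the two texts force opposite actions.

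Third, the Table 3 note sends potentially immune events to 5.6.1.1, where Table 6 withholds at grade 3. That softens the hematologic conflict but does not remove it, because the note offers further information and does not override the row. At grade 2, holding satisfies both Table 6 and the appendix.

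Fourth, there are safeguards. Section 5.6.1.1 requires immediate discussion with the sponsor for immune events of grade 2 or higher. Table 10 requires advance approval of rechallenge after a serious event that the drug may have caused. Section 5.2.1.2 says that subjects with a "recurrence of the same severe or life-threatening event at the same grade or greater with re-challenge of MK-3475 should be discontinued from trial treatment". These reduce the risk. But the sponsor discussion carries no criterion, the rechallenge approval refers back to the protocol's dose-modification guidelines, and the recurrence rule acts only after a second event.

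Finally, the appendix is not flawless. Its grade 3 hepatic block adds a 12-week steroid-taper stop, which is redundant if the drug has already been stopped permanently. Together with the unclear hypothyroidism text, this argues against simply ranking the appendix above Tables 3 and 6, which would also reverse the appendix's own deference.

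**Conclusion.** The body and Appendix 13.4 differ in the action for the same drug-related immune event: restart permitted against permanent stop in seven named event-by-grade combinations. Within the body, Tables 3 and 6 differ on holding at grade 3 for immune hematologic events. The less protective body rules govern on a plain reading, with some ambiguity left.

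A reader might go on to infer an effect on the MTD or on DLT counts. The documents do not support that: the DLT criteria in section 9.1 turn mainly on the type and grade of the event, and nothing says how often these events would occur. No such effect is claimed.

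The conclusion assumes that the event is judged related to MK-3475, as the appendix requires, and that Table 6's withhold leaves restart open once steroids are tapered. This is a cheap improvement, with moderate confidence: the textual difference is clear, and the uncertainty lies in precedence and in how far the existing safeguards already contain the risk.

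**What to change.** Amend the protocol body only, for events judged related to MK-3475:

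1. Limit Table 3's no-hold row for hematologic grades 1-3 to events not considered immune-related.
2. Add rows to Table 6. Listed immune hematologic disorders (Appendix 13.4, section 3.4): hold at grades 2-3, permanently discontinue at grade 4. Hepatic, neurologic and renal immune events: permanently discontinue at grades 3-4.
3. State in 5.2.1.2 and 5.6.1.1 that event-specific body rules (5.6.1, 5.6.1.2 and the new Table 6 rows) govern over the general rows of Tables 3 and 6 and over Appendix 13.4. This agrees with the appendix's deference to the protocol and keeps the stricter enterocolitis stop in 5.6.1.
4. Have the sponsor state the action for grade 3-4 hypothyroidism explicitly.

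The relatedness condition keeps anemia judged due to platinum/etoposide in Part A out of the new rows. Grade 4 endocrine, ocular, skin and other events have no row here. If the sponsor does not want the general rows to apply to them, it can add rows in the same amendment.

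The cost is edits to two tables, one precedence sentence in two sections and one sponsor decision, with no added procedures or patients. The downside is possibly a few more permanent discontinuations.

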5.2.2 Timing of Dose Administration

Trial treatment should be administered on Day 1 of each cycle after all procedures/assessments have been completed as detailed on the Trial Flow Chart (Section 6.0). Trial treatment may be administered up to 3 days before or after the scheduled Day 1 of each cycle due to administrative reasons.

All trial treatments will be administered on an outpatient basis.

MK-3475 will be administered as a 30 minute IV infusion (treatment cycle intervals may be increased due to toxicity as described in Section 5.2.1.2). Sites should make every effort to target infusion timing to be as close to 30 minutes as possible. However, given the variability of infusion pumps from site to site, a window of -5 minutes and +10 minutes is permitted (i.e., infusion time is 30 minutes: -5 min/+10 min).

The Procedures Manual contains specific instructions for MK-3475 dose calculation, reconstitution, preparation of the infusion fluid, and administration.

5.2.3 Trial Blinding/Masking

This is an open-label trial; therefore, the Sponsor, investigator and subject will know the treatment administered.

5.3 Stratification

There is no stratification for this trial.

5.4 Concomitant Medications/Vaccinations (allowed & prohibited)

Medications or vaccinations specifically prohibited in the exclusion criteria are not allowed during the ongoing trial. If there is a clinical indication for one of these or other medications or vaccinations specifically prohibited during the trial, discontinuation from trial therapy or vaccination may be required. The investigator should discuss any questions regarding this with the Sponsor. The final decision on any supportive therapy or vaccination rests with the investigator and/or the subject's primary physician. However, the decision to continue the subject on trial therapy or vaccination schedule requires the mutual agreement of the Investigator, the Sponsor, and the subject.

5.4.1 Acceptable Concomitant Medications

All treatments that the investigator considers necessary for a subject's welfare may be administered at the discretion of the investigator in keeping with the community standards of medical care. All concomitant medication will be recorded on the case report form (CRF) including all prescription, over-the-counter (OTC), herbal supplements, and IV medications and fluids. If changes occur during the trial period, documentation of drug dosage, frequency, route, and date may also be included on the CRF.

All concomitant medications received within 28 days before the first dose of trial treatment and 30 days after the last dose of trial treatment should be recorded. Concomitant medications administered after 30 days after the last dose of trial treatment should be recorded for SAEs and ECIs as defined in Section 7.2.

5.4.2 Prohibited Concomitant Medications

Subjects are prohibited from receiving the following therapies during the Screening and Treatment Phase (including retreatment for post-complete response relapse) of this trial:

- Anti-cancer systemic chemotherapy or biological therapy
- Immunotherapy not specified in this protocol
- Chemotherapy not specified in this protocol
- Investigational agents other than MK-3475
- Live vaccines within 30 days prior to the first dose of trial treatment and while participating in the trial. Examples of live vaccines include, but are not limited to, the following: measles, mumps, rubella, chicken pox, yellow fever, rabies, BCG, and typhoid (oral) vaccine. Seasonal influenza vaccines for injection are generally killed virus vaccines and are allowed; however intranasal influenza vaccines (e.g. Flu-Mist®) are live attenuated vaccines, and are not allowed.

- Glucocorticoids for any purpose other than to modulate symptoms from an event of clinical interest of suspected immunologic etiology. The use of physiologic doses of corticosteroids may be approved after consultation with the Sponsor.

Subjects who, in the assessment by the investigator, require the use of any of the aforementioned treatments for clinical management should be removed from the trial. Subjects may receive other medications that the investigator deems to be medically necessary.

The Exclusion Criteria describes other medications which are prohibited in this trial.

There are no prohibited therapies during the Post-Treatment Follow-up Phase.

5.5 Correlative Studies relating to immunologic response:

The immunotherapy platform will perform immune monitoring, including but not limited to evaluation of CD4 and CD8 T cells in peripheral blood and available tumor samples as previously published, 19,22. All samples will be collected and analyzed as per a separate IRB-approved lab protocol.

5.5.1. Tumor tissues

Tumor tissue collected for diagnostic purposes within 3 months of study entry will be banked under an IRB-approved laboratory protocol and ten to thirty unstained slides or fresh frozen tumor from available tissues will be collected for baseline immune system testing before radiation treatment

Optional biopsy after the completion of radiation therapy:

A biopsy will be done (optional) within 7 days after completion of radiation therapy for immune response monitoring.

